One of the safety endpoints is the rebound phenomenon. Rebound may signify a severe deterioration of psoriasis that is significantly worse than before the treatment was initiated or a change in the character of the psoriasis (e.g., from plaque to pustular form), or both. Per the Committee for Human Medicinal Products (CHMP) guideline on clinical investigation of medicinal products indicated for treatment of psoriasis (23), rebound is defined as "worsening of psoriasis over baseline value (e.g. PASI>125%) or new pustular, erythrodermic or more inflammatory psoriasis occurring within 2 months of stopping therapy. A simple worsening of psoriasis beyond 2 months of therapy may represent the natural course of the disease (relapse) rather than a rebound associated with drug". The National Psoriasis Foundation Medical Advisory Board (US) has also proposed a standard definition of rebound (24). Rebound is said to occur if the PASI is 125% or greater than baseline, or if new generalized pustular, erythrodermic or more inflammatory psoriasis occurs within 3 months of stopping therapy. However, these definitions may not be optimal in patients with mild disease, with low PASI, where even a minor worsening in disease severity may fulfill the criteria for PASI >125%, without in fact being a severe and sudden worsening which is characteristic of rebound. Therefore, for the purpose of this trial, rebound will be defined as (i) an m-PASI ≥ 12 AND an increase in m-PASI of $\geq 125\%$ of the baseline value, or (ii) new pustular, erythrodermic or more inflammatory psoriasis either a) within 2 months after discontinuation of once-daily treatment in the initial open-label phase, b) within 2 months after discontinuation of once-daily relapse treatment, or c) within 2 months after end of maintenance treatment (up to Visit FU3). Hence, only psoriasis that becomes considerably worse than it has previously been will be considered as rebound.

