11.3.6.2 Rebound

Rebound will be defined as (i) an m-PASI ≥ 12 AND an increase in m-PASI of $\geq 125\%$ of the baseline value, or (ii) new pustular, erythrodermic or more inflammatory psoriasis either a) within 2 months after discontinuation of once-daily treatment in the initial open-label phase, b) within 2 months after discontinuation of once-daily relapse treatment, or c) within 2 months after end of maintenance treatment (up to Visit FU3)

Number of rebounds within two months after entering the maintenance phase will be summarised by treatment group in a table.

Number of rebounds occurring after the first two months of maintenance treatment (i.e. including the follow-up period) will be summarised by treatment group in another table.

Subjects with m-PASI $\geq 125\%$ of baseline (Visit1) score and cases of rebound will be listed.

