11.3.8 General Principles

All significance tests will be two-sided using the 5% significance level. All confidence intervals will be presented with 95% degree of confidence.

An observed cases approach will be used for tabulations of data by visit (i.e. involving only those subjects who attended each specific visit).

Categorical data will be summarised using the number and percentage of subjects in each category and treatment group. Continuous data will be summarised using the mean, median, standard deviation (SD), minimum and maximum values.

All the analyses specified in the protocol will be reviewed in relation to the blinded data actually obtained and the statistical analysis plan update will be finalised before breaking the randomisation code.

The randomisation is stratified by treatment group, trial site, HPA axis testing and disease severity at baseline as factors. Usually, the statistical analysis of efficacy parameters takes all the stratification factors into account. However, the HPA axis test is a safety parameter, which is only determined at a small subset of sites and subjects. Hence stratification by HPA axis test is not applicable for all sites. Also, it is expected that two subjects per site will be randomised. This means that a statistical model having HPA axis testing as a factor may not converge, depending on whether subjects participating in the HPA axis test drop out. Furthermore, the inclusion criteria for participating in the HPA axis test are “Moderate” or “Severe” in the baseline PGA assessment and a baseline BSA between 10 and 30%. Including the stratification factor HPA axis testing would therefore introduce a confounding with the

stratification according to baseline PGA as well as sites. Therefore the stratification according to HPA axis testing is not included in the statistical analyses.

Any changes from the statistical analysis planned in this clinical trial protocol will be described and justified in a protocol amendment/the statistical analysis plan update and/or in the clinical trial report dependent on the type of deviation.

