5.5.9	Laboratory Data	36
5.6	General Principles	37
5.6.1	Pooling of Trial Sites	37
5.6.2	Handling of Drop-outs and Missing Values	38
5.6.3	Incomplete dates	38
5.6.4	Multiplicity adjustment	38
5.6.5	Treatment Labels	39
5.7	Changes to the analyses described in the protocol	40
	Appendix I	47
	Appendix II	67

Trial ID: LP0053-1004	Date: 15-JUL-2019	Version: 1.0 Page 6 of 177
------------------------------	--------------------------	-------------------------------

3 List of Abbreviations

ACTH	Adrenocorticotropic Hormone
AE	Adverse Event
ATC	Anatomical Therapeutic Chemical
BSA	Body Surface Area
CPM	Clinical Project Manager
CPMP	Committee for Proprietary Medicinal Products
CRA	Clinical Research Associate
CRF	Case Report Form
CRO	Contract Research Organisation
DK	Denmark
DLQI	Dermatology Life Quality Index
eCRF	Electronic Case Report Form
eDiary	Electronic Diary
EU	European Union
GCP	Good Clinical Practice
ICH	International Conference on Harmonisation
IEC	Independent Ethics Committee
IMP	Investigational Product
IRB	Institutional Review Board
m-PASI	Modified Psoriasis Area Severity Index
MedDRA	Medical Dictionary for Regulatory Activities
MMRM	Mixed effect Model Repeat Measurement
ML	Maximum Likelihood
PASI	Psoriasis Area Severity Index
PASI 75	A 75% reduction in the modified Psoriasis Area Severity Index
PGA	Physician's Global Assessment of Disease Severity
PRO	Patient Reported Outcome
PSI	Psoriasis Symptom Inventory
REML	Restricted Maximum Likelihood
SAE	Serious Adverse Event

SAP	Statistical Analysis Plan
SD	Standard Deviation
SGA	Subject's global assessment of disease severity
SOC	System Organ Class
SOP	Standard Operating Procedure
UNS	Unscheduled Visit

4 Introduction

The statistical analysis will be performed as outlined in the Clinical Trial Protocol including amendments. This statistical analysis plan, prepared before the unblinding of the trial, but after the blind review of the data, contains a more technical and detailed elaboration of some points in the statistical analysis described in the Clinical Trial Protocol. Deviations from the planned data presentation and analysis are also described in section [5.7](#). Furthermore, the analysis sets, which are to be used for the statistical analysis, are presented.

5 Statistical Analysis

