5.3 Baseline Considerations

5.3.1 Baseline definition

As described in the protocol, baseline is defined as the measurement taken at screening or visit 1.

The maintenance phase baseline is defined as the last available measurement collected at randomisation (visit 2).

Baseline for rebounds will be handled differently as described in section [5.5.4](#).

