5.5.4 Rebound

Rebounds will be defined as described in the protocol. The baseline value will be the m-PASI value measured at the start of the rebound follow-up period. A rebound follow-up period is defined as either (i) 2 months after discontinuation of open-label phase treatment, (ii) 2 months after discontinuation of relapse treatment, or (iii) 2 months after discontinuation of maintenance treatment (up to Visit FU3).

Number of rebounds occurring within the first 2 months after discontinuation of the open-label phase treatment, and number of rebounds occurring within 2 months after discontinuation of relapse treatment will be summarised by treatment group.

Number of rebounds occurring within two months after discontinuation of maintenance treatment will be summarised by treatment group.

Cases of rebounds will be listed.

More details for the tables and listings can be found in [Appendix I](#) and [Appendix II](#).

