Table 3-66 Frequent adverse events ($\geq 1\%$ in any treatment group) during the first 28 weeks of the randomised phase by SOC, preferred term, and randomised treatment: safety analysis set

Table 3-67 Frequent adverse events ($\geq 1\%$ in any treatment group) during the last 32 weeks of the randomised phase by SOC, preferred term, and randomised treatment: safety analysis set

Table 3-68 Frequent adverse events ($\geq 1\%$ in any treatment group) during the total maintenance phase by SOC, preferred term, randomised treatment, and rescue medication: safety analysis set

Table 3-69 Frequent adverse events ($\geq 1\%$ in any treatment group) during the first 28 weeks of the maintenance phase by SOC, preferred term, randomised treatment, and rescue medication: safety analysis set

Table 3-70 Frequent adverse events ($\geq 1\%$ in any treatment group) during the last 24 weeks of the maintenance phase by SOC, preferred term, randomised treatment, and rescue medication: safety analysis set

Table 3-71 Summary of rebounds occurring within 2 months after discontinuing open-label phase treatment or relapse treatment: safety analysis set

Table 3-72 Summary of rebounds occurring within 2 months after discontinuation of maintenance treatment : safety analysis set

Table 3-73 Physician's assessment of local safety and tolerability by visit in open-label phase: open-label safety analysis set

Table 3-74 Shift table for physician's assessment of local safety and tolerability from start to end of open-label phase: open-label safety analysis set

Table 3-75 Physician's assessment of local safety and tolerability by visit not related to relapse: safety analysis set

Table 3-76 Physician's assessment of local safety and tolerability by visit for start of relapse: safety analysis set

Trial ID: LP0053-1004	Date: 15-JUL-2019	Version: 1.0 Page 60 of 177
------------------------------	--------------------------	--------------------------------

Table 3-77 Physician's assessment of local safety and tolerability by visit for end of relapse: safety analysis set

Table 3-78 Shift table for physician's assessment of local safety and tolerability from start of relapse to end of relapse by visit for start of relapse: safety analysis set

Table 3-79 Subject's assessment of local safety and tolerability by visit in open-label phase: open-label safety analysis set

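### SAP 5.5.4 measures rebound against the m-PASI at the start of each follow-up window instead of Visit 1, without a reason or a 5.7 entry, so a subject milder than at entry can count as a rebound

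*SAP*

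**What the plan says.** Protocol 11.3.6.2 (repeated in 3.3.3 and 9.3.6) gives two routes to rebound within two months of stopping open-label, relapse or maintenance treatment. Criterion (i) requires an m-PASI of at least 12 and, jointly, a rise defined as 125% relative to baseline. Criterion (ii) is a new pustular, erythrodermic or more inflammatory form.

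The definition sentence does not name the baseline visit. The listing specified in the same section does: subjects whose m-PASI reaches 125% "of baseline (Visit1) score and cases of rebound will be listed". Protocol 3.3.3 states the purpose: "Hence, only psoriasis that becomes considerably worse than it has previously been will be considered as rebound".

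SAP 5.3.1 says: "As described in the protocol, baseline is defined as the measurement taken at screening or visit 1". It then adds: "Baseline for rebounds will be handled differently as described in section" 5.5.4. That section says rebound is defined as in the protocol, and continues: "The baseline value will be the m-PASI value measured at the start of the rebound follow-up period". It gives no reason.

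On documenting changes, the SAP Introduction (section 4) says: "Deviations from the planned data presentation and analysis are also described in section" 5.7. Protocol 11.3.8 says: "Any changes from the statistical analysis planned in this clinical trial protocol will be described and justified". The table in SAP 5.7 covers compliance (5.3.4) and the efficacy and patient-reported sections (5.4); it has no row for 5.5.4.

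The results go into Table 3-71, "Summary of rebounds occurring within 2 months after discontinuing open-label phase treatment or relapse treatment: safety analysis set", Table 3-72 (after maintenance treatment) and Listing 7-9.

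**The concern.** The SAP says it keeps the protocol's definition but changes the value the definition depends on. The protocol joined two conditions so that only disease clearly worse than before treatment would count. Measured from a nearly clear skin score, the relative condition is met by almost any return of disease, and the floor of 12 is left to do the work alone.

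Incidence of rebound is a named safety assessment (Protocol 5.3), and every subject is followed for 8 weeks for it (Protocol 6.1.5). Table 3-71 could include subjects who have only returned to entry severity or less. Table 3-72 could omit a subject who meets the Visit 1 rule. Investigators report rebound as an adverse event from the protocol's wording (9.3.6); if they take baseline to be Visit 1, the derived counts and the reported events could disagree with no stated explanation.

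**Working it through.** **Which baseline does the protocol mean?**
- The 125% listing in 11.3.6.2 names Visit 1.
- Protocol 8.16.3 starts m-PASI assessment at baseline, identified as Visit 1.
- Protocol 11.3.4.4 separates the baseline m-PASI from the value at randomisation four weeks later. Randomisation is where the first rebound window opens, so the protocol does not call that value baseline.
- Protocol 3.3.3 describes rebound as worse than the disease was before treatment began.
- SAP 5.3.1 agrees for every purpose except rebound.

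**Formula.** Protocol 8.16.3 weights arms, trunk and legs by 0.2, 0.3 and 0.4. With the same sign total T (0 to 12) and extent score E (0 to 6) in every area, m-PASI = 0.9 × T × E. The maximum is 0.9 × 12 × 6 = 64.8, which reproduces the protocol's figure.

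**Cut-off for criterion (i)** with baseline b is max(12, k × b). The main reading is k = 1.25 (a level of 125% of baseline, as in the listing). If an increase of 125% is meant, k = 2.25. The floor decides alone when b ≤ 12/1.25 = 9.6, or b ≤ 12/2.25 = 5.33.

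**Where do windows start?** Randomised subjects enter at PGA clear or almost clear (Protocol 6.1.3), as do those who continue after rescue (6.1.4). Assume almost clear means each sign scores at most 1, so T ≤ 3:

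| Extent in every area | Highest start | Cut-off, k = 1.25 | Cut-off, k = 2.25 |
|---|---|---|---|
| <10% (E = 1) | 2.7 | 12 | 12 |
| 10–29% (E = 2) | 5.4 | 12 | 12.15 |
| 30–49% (E = 3) | 8.1 | 12 | 18.2 |

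On the main reading the relative condition never matters from such a start. On the other reading it matters only near the top of the range.

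**Example A: counted although milder than at entry.** Visit 1: T = 9, E = 2, so 0.9 × 9 × 2 = 16.2. Affected body surface is at most 29%, because no area exceeds 29%, so the subject fits the 30% cap. Window start 2.7. Later T = 7, E = 2: 12.6, and 12.6/16.2 − 1 = −22%.
- SAP cut-off: 12 on either reading. Rebound.
- Visit 1 cut-off: 1.25 × 16.2 = 20.25 (2.25 × 16.2 = 36.45). Not rebound.

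**Example B: worse than entry, but below 125% of it.** Visit 1: T = 6, E = 2, so 10.8. Later 12.6 from a low start.
- SAP cut-off: 12. Rebound.
- Visit 1 cut-off: 13.5 (24.3). Not rebound.

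**Example C: missed by the SAP.** Visit 1: T = 9, E = 1, so 8.1. Relapse confirmed at Visit 15 (a case Protocol 6.1.5 provides for) with T = 6, E = 2, so 10.8. Later 12.6.
- Visit 1 cut-off: max(12, 10.1) = 12. Rebound.
- SAP cut-off: 1.25 × 10.8 = 13.5. Not rebound.
- With k = 2.25 the cut-offs are 18.2 and 24.3, so a score of 21.6 (T = 12, E = 2) would be the missed case.

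**Who cannot be affected?** With extent below 10% in every area the maximum is 0.9 × 12 × 1 = 10.8, so criterion (i) cannot be met under either baseline. From a low start, the two rules agree for Visit 1 scores up to 9.6 (5.33). Counting a score at or below entry severity needs a Visit 1 m-PASI of at least 12; with extent 10–29% everywhere that means T ≥ 7, because T = 6 gives only 10.8.

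**The case against.** The strongest reply is that little may change in practice. The protocol's own rule also reduces to the floor of 12 for Visit 1 scores up to 9.6. Reclassification from a low start needs a higher entry score and a rise to 12 within two months, with visits every four weeks and rescue starting at PGA mild. The documents give no m-PASI distribution, the examples are constructed, and the tables are untested. All of this stands, and it limits the size of the problem.

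A second reply is that the change is not hidden. It appears in both 5.3.1 and 5.5.4. The Introduction presents 5.7 as an additional place for deviations, and Protocol 11.3.8 also allows justification in the clinical trial report. Section 5.7 omits other safety changes too, such as dropping the adverse event tests. The missing row therefore fits a pattern, but the adverse event section explains its change in the text and 5.5.4 does not. The missing reason is the weightier fault.

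Third, the definition sentence never says Visit 1, so the SAP could be said to settle a loose term. The surrounding text leaves little room for that reading.

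Three smaller points also hold in part. The safety analysis set may contain a few subjects randomised in error without treatment success (SAP 5.2, Shell 2), so not everyone starts clear or almost clear. Investigator-reported rebound still reaches the adverse event tables. The SAP nowhere expressly withdraws the Visit 1 listing; it has no entry of its own in Appendix I, though Listing 6-6 would let a reader rebuild it.

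**Conclusion.** The concern holds and should be fixed. SAP 5.5.4 replaces the Visit 1 baseline with a moving one, gives no reason and omits it from 5.7. As written, the rule can label a subject 22% below entry severity as a rebound, contrary to the protocol's stated intent, and can miss one who meets the Visit 1 rule.

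The reading of the texts and the arithmetic are firm, and the conclusion is the same on either reading of the 125%. The window-start table assumes that almost clear means no sign scores above 1; the worked examples use the same signs and extent in every area. The floor of 12 is kept and criterion (ii) is untouched. How many subjects change classification cannot be learned from the documents.

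**What to change.** In SAP 5.5.4:
- Define the baseline for criterion (i) as the Visit 1 m-PASI in Tables 3-71 and 3-72 and Listing 7-9, and use the window start only to time the two months.
- State one arithmetic reading of the 125% condition.
- Restore the protocol's listing of subjects at or above 125% of their Visit 1 score.

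If the window-start version is wanted as well, declare and justify it in 5.7 and show it as supplementary.

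The cost is one sentence, one derivation line and one listing, plus one row in 5.7 if both versions are kept. No new data are needed: m-PASI is scheduled at Visit 1 and already appears in Listing 6-6.

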3.3.2 Research hypothesis

The present trial will evaluate the efficacy and safety of LEO 90100 used as a long-term twice-weekly maintenance therapy compared with vehicle. Following an initial 4-week period where all subjects will be treated with LEO 90100 in accordance with the currently approved labeling, they will be randomised to receive either LEO 90100 or vehicle per the twice weekly maintenance regimen for 52 weeks. In cases of relapse, affected subjects in either treatment group will again receive LEO 90100 to apply once daily for 4 weeks on active areas on trunk and limbs. Thus, the vehicle arm will also utilise re-treatment as needed, similar to the use in clinical practice for the licensed calcipotriol/BDP products. Thus, the trial will compare two ways of using LEO 90100: a proactive approach with fixed twice-weekly maintenance regimen with a conventional, reactive approach. The research hypothesis is that the proactive twice-weekly maintenance use of LEO 90100 will prolong the time to relapse and reduce the frequency of relapses in subjects with psoriasis vulgaris, as compared with vehicle while still maintaining a favorable safety profile. It is further hypothesized with regard to long-term efficacy that subjects who receive LEO 90100 twice weekly will demonstrate superior response to those randomised to receive vehicle, as measured by the number of days in remission.

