5.3 Safety assessments

- Adverse events of concern associated with long-term corticosteroid use
- Incidence of rebound (as defined in section [11.3.6.2](#))
- Local safety and tolerability assessment scores
- Effect on calcium metabolism, based on change from baseline in serum calcium and spot urinary calcium at Week 4 and the end of trial
- Effect on HPA axis (in a subset of subjects with disease involvement of between 10 and 30% of BSA), based on serum cortisol ≤ 18 mcg/dL 30 minutes after cosyntropin injection at Week 4, Week 28, and end of trial (Week 56) or early withdrawal.

[figure not shown]
Exposure and standard safety data will be reported as described in sections [11.3.3](#) and [11.3.6](#).

6 Trial Design

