11.1 Determination of Sample Size

For subjects with psoriasis vulgaris, the number of relapses per year is assumed to be between 4 and 8. We assume that the time to event (first relapse) is a Poisson process, i.e. that events occur continuously and independently at a constant rate. Then the time between events is given by the exponential distribution. Time to event is analysed by means of the hazard function, which can be thought of as the probability of experiencing an event now if you have not experienced one already. [Table 16](#) shows the mean and median waiting times as well as hazards according to number of relapses per year.

Table 16: Mean and median waiting times and hazards according to number of relapses per year

	Number of relapses per year		
	4	6	8
Mean waiting time (weeks)	13.00	8.67	6.50
Median waiting time (weeks)	9.01	6.01	4.51
Hazard	0.077	0.115	0.154

The drop-out rate observed in a long-term trial with calcipotriol/BDP ointment (MCB 0102 INT) was about 30 % over 52 weeks. Assuming an exponential decline this corresponds to a median waiting time for drop out at about 101 weeks. We assume that the same will be the case in this trial and that between 4 to 8 relapses will occur per year in the vehicle group.

A 30 percent reduction in hazard, i.e. a hazard ratio of 0.7 for active treatment group relative to vehicle group is considered to be of clinical interest.

With the above assumptions it follows using a two sample survival test that for detecting a hazard ratio of 0.7 for active treatment group relative to vehicle group, between 178 and 190 subjects per group are needed in order to obtain a power of 90% for a 5% significance level. Thus, 380 subjects should be randomised.

In previous trials in similar populations, approximately 48% subjects treated with LEO 90100 aerosol foam achieved treatment success after 4 weeks of treatment. Assuming a binomial distribution with 48 % probability of success it is estimated that 832 subjects should be included in the trial in order to have 90 % probability of achieving at least 380 subjects to be randomised.

For the HPA axis testing, the aim is to achieve approximately 25 subjects undergoing HPA axis testing after 52 weeks of exposure.

The total number of subjects treated in the trial should also be sufficient to comply with ICH E1 regarding long-term safety. The aim is to achieve at least 300 subjects with 26 weeks of exposure and at least 100 subjects with 52 weeks of exposure.

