Mean (SD)	xx.x (xx.x)	xx.x (xx.x)	xx.x (xx.x)
Median	xx.x	xx.x	xx.x
Q1;Q3	xx.x;xx.x	xx.x;xx.x	xx.x;xx.x
Min;Max	xx.x;xx.x	xx.x;xx.x	xx.x;xx.x

Shell 101: Summary of rebounds occurring within 2 months after discontinuing open-label phase treatment or relapse treatment: safety analysis set

	LEO 90100 (n=xxx)	Vehicle (n=xxx)
Within 2 months after discontinuation of open-label treatment:		
Number of rebounds	xxx	xxx
Number of subjects	xxx	xxx
Mean (SD)	xx.x (xx.x)	xx.x (xx.x)
Median	xx.x	xx.x
Q1;Q3	xx.x;xx.x	xx.x;xx.x
Min;Max	xx.x;xx.x	xx.x;xx.x
Within 2 months after discontinuation of relapse treatment:		
Number of rebounds	xxx	xxx
Number of subjects	xxx	xxx
Mean (SD)	xx.x (xx.x)	xx.x (xx.x)
Median	xx.x	xx.x
Q1;Q3	xx.x;xx.x	xx.x;xx.x
Min;Max	xx.x;xx.x	xx.x;xx.x

Shell 102: Summary of rebounds occurring within 2 months after discontinuing of maintenance treatment: safety analysis set

	LEO 90100 (n=xxx)	Vehicle (n=xxx)
Within 2 months after discontinuation of maintenance treatment:		
Number of rebounds	xxx	xxx
Number of subjects	xxx	xxx
Mean (SD)	xx.x (xx.x)	xx.x (xx.x)
Median	xx.x	xx.x
Q1;Q3	xx.x;xx.x	xx.x;xx.x
Min;Max	xx.x;xx.x	xx.x;xx.x

Signature Page for TMF-000023733 v1.0

Reason for signing: Approved	Manage Name: PPD Capacit Date of signature: 15-Jul-2019 08:57:51 GMT+0000	(s)
Reason for signing: Approved	Manage Name: PPD Capacit Date of signature: 15-Jul-2019 09:16:48 GMT+0000	dict(s)
Reason for signing: Approved	QC App Name: PPD Capacit Date of signature: 15-Jul-2019 09:20:55 GMT+0000	

Electronic signatures made within eTMF LEO are considered to be a
legally binding equivalent of traditional handwritten signatures.

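### The by-arm count of rebounds after relapse treatment has no denominator of relapse courses stopped, so it cannot show whether rebound risk per stopped course differs between arms

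*SAP*

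**What the plan says.** Protocol 5.3 names "Incidence of rebound" among the safety assessments. Protocol 11.3.6.2 defines rebound relative to three stopping points (initial open-label treatment, a relapse course, maintenance treatment) and plans counts by treatment group.

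SAP 5.5.4 opens a 2-month follow-up period at each stopping point. For relapse courses it says the "number of rebounds occurring within 2 months after discontinuation of relapse treatment will be summarised by treatment group". The matching output is Shell 101, titled "Summary of rebounds occurring within 2 months after discontinuing open-label phase treatment or relapse treatment: safety analysis set". Its second block, headed "Within 2 months after discontinuation of relapse treatment", has rows for number of rebounds, number of subjects, mean (SD), median, quartiles and range for each arm. There is no row for courses stopped and no rate, and the shell does not say what the subject count or the mean refer to. SAP 5.7 lists no change for rebound.

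Protocol 6.1.1 gives every confirmed relapse one 4-week course of rescue treatment, in either arm. Protocol 3.3.2 hypothesises that twice-weekly LEO 90100 "will prolong the time to relapse and reduce the frequency of relapses in subjects with psoriasis vulgaris, as compared with vehicle".

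**The concern.** For rebound after relapse treatment the unit at risk is a stopped course. A subject with no relapse contributes none; a subject with four relapses can contribute four. If the trial works as hypothesised, the vehicle arm accumulates more stopped courses and therefore more opportunities for rebound. A lower count on LEO 90100 could then be read as a lower tendency to rebound when the same 4-week course is stopped, when it may only reflect fewer courses. Conversely, a truly higher risk per stopped course on LEO 90100 could be masked.

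The SAP accepts the underlying principle elsewhere. Section 5.5.3 drops statistical tests on the percentage of subjects with adverse events because follow-up may differ by arm, and relapses and adverse events are given rates per 100 patient-years. Rebound after relapse treatment has no comparable adjustment for opportunity.

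**Working it through.** **Inputs.** From Protocol 11.1: vehicle relapse rate r = 4 to 8 per year; "a hazard ratio of 0.7 for active treatment group relative to vehicle group is considered to be of clinical interest"; drop-out of 30% over 52 weeks, exponential. From Protocol 6.1.1: 52 weeks of maintenance, 1:1 allocation, 4-week courses. From SAP Table 8: 132 + 55 + 52 + 68 + 56 + 68 + 114 = 545 randomised, about 272 per arm. Not in the documents, so assumed: the probability that a course ends in exit because the subject is not clear or almost clear; the rebound risk per stopped course; and constant hazards after each course.

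**Plan's own figure.** Protocol 11.1 gives 178 to 190 subjects per group "in order to obtain a power of 90% for a 5% significance level".
- Drop-out hazard: d = −ln(0.7)/52 = 0.00686 per week, median about 101 weeks, as stated.
- Events (Schoenfeld): 4(1.960 + 1.282)²/(ln 0.7)² ≈ 331. Freedman's formula gives 338.
- P(event) = λ/(λ + d) × [1 − exp(−52(λ + d))], averaged over arms with λ = r/52 and 0.7r/52: 0.878 at r = 4 and 0.947 at r = 8.
- Per group: 189 and 175 (Schoenfeld), or 193 and 179 (Freedman).

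The stated range is reproduced to within 3%, so the inputs are read correctly.

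**Courses per subject, no exits.** A long-run approximation treats each cycle as a mean remission of 52/r weeks (divided by 0.7 on LEO 90100) plus a 4-week course. The course ratio is then (52/r + 4)/(52/(0.7r) + 4):
- r = 4: 17.00/22.57 = 0.75
- r = 6: 12.67/16.38 = 0.77
- r = 8: 10.50/13.29 = 0.79

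Simulating the alternating remission and course periods over 52 weeks with the stated drop-out gives the same ratios:

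| Vehicle relapses/year | Courses per subject, LEO 90100 | Courses per subject, vehicle | Ratio | Courses at 272 per arm |
|---|---|---|---|---|
| 4 | 1.96 | 2.60 | 0.75 | 531 vs 707 |
| 6 | 2.70 | 3.50 | 0.77 | 733 vs 953 |
| 8 | 3.34 | 4.24 | 0.79 | 907 vs 1153 |

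These are courses started, each stopping at 4 weeks or at drop-out. Counting only courses completed within the 52 weeks lowers the levels (about 1.8 to 3.0 against 2.4 to 3.9) but leaves the ratio at 0.75 to 0.79. With equal risk per stopped course, the expected ratio of rebound counts equals the course ratio, that is, 21% to 25% fewer on LEO 90100. Rebounds per stopped course would have an expected ratio of 1.00.

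**Effect of exit after a failed course** (assumed probabilities per course, r = 4 to 8):

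| Exit, LEO 90100 | Exit, vehicle | Expected count ratio |
|---|---|---|
| 0% | 0% | 0.75–0.79 |
| 10% | 10% | 0.77–0.82 |
| 20% | 20% | 0.80–0.86 |
| 52% | 52% | 0.87–0.93 |
| 10% | 20% | 0.87–1.00 |
| 10% | 30% | 0.98–1.19 |

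With a hazard ratio of 1 and equal exit, the ratio is 1.00.

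**Chance variation.** At an assumed 1% risk per course, no exits and 272 per arm, expected counts are 5.3 vs 7.1, 7.3 vs 9.5 and 9.1 vs 11.5. Treating counts as Poisson, LEO 90100 shows strictly fewer rebounds with probability about 64% to 67%. At 5% risk this rises to 85% to 88%.

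**Overlapping windows.** Taking 2 months as 8.7 weeks, the chance of a new relapse inside a window is 1 − exp(−8.7λ): 49% to 74% on vehicle and 37% to 61% on LEO 90100. A further course may therefore be stopped before the first window closes, and SAP 5.5.4 does not say to which stop a rebound then belongs.

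**The case against.** The strongest reply is that the by-arm count is not an artefact. Protocol 3.3.2 frames the trial as a comparison of proactive and reactive use of LEO 90100. Rebounds per randomised subject compare those strategies with randomisation intact, and avoiding rebounds by avoiding rescue courses is a real benefit. A rate per course conditions on relapse after randomisation: on LEO 90100 only subjects who relapsed despite active maintenance contribute. This stands. It means the rate should supplement the count, not replace it.

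Second, the information is nearly available. Shells 72 and 78 give the total number of ended relapses by arm in the safety analysis set, rebounds are listed individually in Listing 7-9, and no test is planned. Rebounds are also adverse events and so enter tables with rates per 100 patient-years. The first part stands and makes the change cheap, but nothing in the plan links those totals to rebound. The patient-year rate does not help: with equal follow-up it keeps the 0.75 to 0.79 ratio, because courses per patient-year are what differ.

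Three stronger readings are tempting but unsupported:
- A reader might infer that the vehicle arm stops more courses by design. The design gives one course per relapse in both arms; the excess is the hypothesis.
- A reader might infer that LEO 90100 is bound to show fewer rebounds. Subjects who fail rescue leave the trial (Protocol 6.1.1), and SAP 5.7 itself considers that withdrawal may be higher on vehicle, which can cancel or reverse the gap. Small counts also leave the observed direction uncertain.
- A reader might infer that the next relapse cuts the 2-month windows short. SAP 5.5.4 contains no such rule; it is silent on overlap.

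**Conclusion.** The point holds as a limited reporting gap. The relapse-treatment block of Shell 101 omits its at-risk unit, and that unit is expected to differ by arm under the trial's own planning assumptions. With hazard ratio 0.7, 4 to 8 vehicle relapses a year and equal risk per stopped course, the expected count ratio is 0.75 to 0.79 without exits and 0.77 to 0.86 with 10% to 20% exit in both arms. Higher exit on vehicle can take it to 1 or beyond. These figures rest on assumed exit probabilities and constant hazards.

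The count answers which strategy produces more rebounds. It does not answer whether stopping a course carries a different rebound risk in the two arms, and in that respect it can mislead in either direction. The primary and secondary efficacy analyses are unaffected. The gap does not extend to the open-label block of Shell 101 or to Table 3-72: open-label treatment stops once per randomised subject and maintenance treatment about once, so the arm n already serves as denominator.

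**What to change.** Keep the counts. In the relapse-treatment block of Shell 101 (Table 3-71) add, for each arm, the number of relapse courses stopped and the number of rebounds per 100 stopped courses. Count each rebound once, against the latest discontinuation before it. State what the subject-count and mean rows refer to, and say whether a course cut off by withdrawal counts as stopped. Label the rate supplementary and descriptive, because it conditions on relapse after randomisation; that limited interpretability is its small downside.

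The cost is two rows and a footnote in one block of one shell. The number of ended relapses by arm is already derived for Shell 72 in the same analysis set, and no new data are needed. The open-label block and Table 3-72 can stay as they are.
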